15.7. Potentially Clinically Significant Abnormalities (PCSA) Criteria

Table 15-3 Potentially Clinically Significant Abnormalities Criteria

CRITERIA for POTENTIALLY CLINICALLY SIGNIFICANT ABNORMALITIES

(From BTD-009536 May 21, 2014)

Parameter	PCSA	Comments
HR	≤ 50 bpm and decrease from baseline ≥ 20 bpm	To be applied for all positions (including missing) except STANDING.
	≥ 120 bpm and increase from baseline ≥ 20 bpm	
SBP	≤ 95 mmHg and decrease from baseline ≥ 20 mmHg	To be applied for all positions (including missing) except STANDING.
	≥ 160 mmHg and increase from baseline ≥ 20 mmHg	
DBP	≤ 45 mmHg and decrease from baseline ≥ 10 mmHg	To be applied for all positions (including missing) except STANDING.
	≥ 110 mmHg and increase from baseline ≥ 10 mmHg	
Weight	$\geq 5\%$ increase from baseline $\geq 5\%$ decrease from baseline	FDA Feb 2007

15.8. Participant-Reported Outcomes (PROs)

Asthma Sleep Disturbance Questionnaire

The Asthma Sleep Disturbance Questionnaire is a PRO measure designed to assess the impact of asthma on participants' sleep. Scores range between 0 to 4 with 0 indicating no impact of asthma on sleep and 4 indicating higher impact of asthma on sleep.

Participants will be instructed to record the severity of the disturbance of their sleep due to asthma as follows:

- 0 = Slept through the night, no asthma symptoms,
- 1 = Slept well, no nighttime awakenings because of asthma, but some asthma symptoms in the morning,
- 2 = Woke up once because of asthma (may or may not include early awakening),
- 3 = Woke up several times because of asthma (may or may not include early awakening),
- 4 = Bad night, awake most of the night because of asthma.

The participants will record their sleep disturbance in an electronic diary, once a day upon awakening.

Asthma Sleep Disturbance Questionnaire data will be provided by CLARIO.

ADSD and ANSD

ADSD and ANSD assess asthma severity based on participant self-report of asthma core symptoms (i.e., difficulty breathing, wheezing, shortness of breath, chest tightness, chest pain and cough).

Both ADSD and ANSD are composed of 6 items rated using an 11-point numeric rating scale (NRS) that ranges from 0 = None to 10 = as bad as you can imagine, which will be completed by participants daily for 11 days before Baseline visit and for 7 days prior each subsequent visit (every night before they go to bed for ADSD and every morning when getting up for ANSD, respectively).

ADSD and ANSD data will be directly provided by CLARIO.

PROMIS Sleep Related Impairment Short Form 8a

The PROMIS is a DSM-5, Level 2, sleep disturbance measure to assess the impact of sleep-related impairment during waking hours. This study uses the 8-item PROMIS Sleep Related Impairment Short Form (PROMIS SF v1.0 Sleep-Related Impairment Short Form 8a).

The questionnaire focuses on self-reported perceptions of alertness, sleepiness, and tiredness during usual waking hours, and the perceived functional impairments during wakefulness associated with sleep problems or impaired alertness. Though Sleep-Related Impairment does not directly assess cognitive, affective, or performance impairment, it does measure waking alertness, sleepiness, and function within the context of overall sleep-wake function. It assesses sleep-related impairment over the past seven days. Each item is rated on a 5-point scale (1 = not at all; 2 = a little bit; 3 = somewhat; 4 = quite a bit; and 5 = very much) with a range in score from 8 to 40 with higher scores indicating greater sleep impairment.

PROMIS raw score is calculated by summing the answers to the 8 items on the short form. All questions must be answered in order to produce a valid score using the scoring tables. PROMIS raw score and T-score will not be calculated if there is no answer for at least one item.

Locate the applicable score conversion in [Table 15.8.1](#), and use this table to translate the total raw score or imputed total score into a PROMIS T-score for each participant. The T-score rescales the raw score into a

standardized score with a mean of 50 and a standard deviation of 10. Therefore, a person with a T-score of 40 is one SD below the mean. The standardized T-score is reported as the final score for each participant.

Table 15.8.1 PROMIS Sleep-Related Impairment conversion table

Raw Score	T-score	Raw Score	T-score
8	30	25	60.3
9	35.1	26	61.3
10	38.7	27	62.3
11	41.4	28	63.3
12	43.6	29	64.3
13	45.5	30	65.3
14	47.3	31	66.3
15	48.9	32	67.3
16	50.3	33	68.4
17	51.6	34	69.5
18	52.9	35	70.7
19	54	36	71.9
20	55.1	37	73.3
21	56.1	38	75
22	57.2	39	76.9
23	58.2	40	80
24	59.3		

PROMIS score will be directly provided by CLARIO.

Sleep diary

Collected daily including 11 days immediately preceding the baseline visit (V2), and daily for 12 weeks (until end of study intervention).

A sleep diary is designed to gather information about participant's daily sleep pattern. Participants are instructed to complete all questions upon awakening each day.

The Sleep Diary is composed of seven generic, participant-reported questions that assess sleep concepts of relevance and importance to adults who report sleep disturbance due to asthma.

The Sleep Diary features two subjective, participant-rated items that use a 0-to-10 NRS to assess sleep quality and feeling rested upon awakening (i.e., restorative sleep). Additional items include the participant-estimated initial sleep attempt time and sleep onset time, number of nighttime awakenings after sleep onset, total time spent awake after sleep onset, and wake time the next day. All questions except the one about

restorative sleep ask participants to recall “last night”; question about restorative sleep asks participants to recall “when they got up for the day today”. Items about sleep quality and restorative sleep are scored; the other items are reported/described separately, as appropriate for each item.

The following variables will be derived from sleep diary:

WASO (min)= Time awake after initial sleep onset but before the final awakening

This is data collected from Question 3 of the Sleep Diary: “Considering all the times you woke up last night, how much time were you awake in total?”

[REDACTED]
[REDACTED]
[REDACTED] [REDACTED] [REDACTED]

Sleep diary data will be directly provided by CLARIO.

[figure not shown]
Asthma Control Questionnaire ([REDACTED] and ACQ-5)

[REDACTED] collects participants assessment of their asthma during the previous week based on 6 questions on a 7-point scale (0 = no impairment to 6 = maximum impairment).
[REDACTED]

The ACQ was designed to measure both the adequacy of asthma control and change in asthma control which occurs either spontaneously or as a result of study intervention. The [REDACTED], with the first 5 items assessing the most common asthma symptoms (corresponding to ACQ-5):

1. frequency in past week awoken by asthma during the night
2. severity of asthma symptoms in the morning
3. limitation of daily activities due to asthma
4. shortness of breath due to asthma
5. wheeze

[REDACTED]
[REDACTED]
[REDACTED]

A global score is calculated as follows:

[figure not shown]
Higher score indicates lower asthma control. Participants with a score below 1.0 reflect adequately controlled asthma and participants with scores above 1.0 reflect inadequately controlled asthma. On the 7-point scale of the [REDACTED], a change or difference in score of 0.5 is the smallest change that can be considered clinically important, corresponding to the Minimal Clinically Important Difference (MCID) defined by the developer. The participants will complete the [REDACTED] as per SoA.

15.9. Clinician-Reported Outcomes (CLINROs)

15.9.1. Clinician Assessments

Spirometry

A spirometer that meets the 2005 ATS/European Respiratory Society (ERS) recommendations will be used. Spirometry should be performed in accordance with these recommendations.

For prebronchodilator measured parameters, including FEV1 and forced vital capacity (FVC), spirometry will be performed before IMP administration and after withholding the standard of care asthma treatment as detailed in the clinical trial protocol which will be verified before performing the measurements.

For post-bronchodilator FEV1, the measurement should follow the steps as that at screening test for reversibility validation.

At all visits, spirometry should be performed before IMP administration, in the morning, if possible. The spirometer provided by the service provider should be used and standard spirometric techniques, including calibration, will be used to perform spirometry at all visits and, whenever possible, the same person should perform the measurements. Afternoon/evening is allowable in the exceptional circumstance when morning spirometry cannot be performed. Spirometry should be done at approximately the same time at each visit throughout the study.

Pulmonary function tests will be measured in the sitting position if possible. If the testing was made with the participant in another position, this should be noted on the spirometry report. For any participant, the position should be consistent throughout the study.

Three measurements fulfilling the ATS acceptability and repeatability criteria should be obtained at each visit. The acceptability criteria must be applied before the repeatability criteria.

Unacceptable maneuvers must be discarded before applying the repeatability criteria. At least 2 acceptable curves must be obtained.

The largest FEV1 and largest FVC should be recorded after the data from all of the acceptable curves have been examined, even if they do not come from the same curve.

The spirometer must be calibrated following the principles of the ATS/ERS guidelines every day that a participant is seen and subjected to spirometry. The calibration records should be kept in a reviewable log. It is preferred that the equipment that is used to calibrate the spirometer (ie, 3-liter syringe) be subjected to a validated calibration according to the manufacturer's specifications. A participant who is unable to complete a successful spirometry effort as defined by ATS criteria or evaluated by the investigator or who didn't meet the eligibility criterion at SV1 can be retested one additional time during the screening period of the study. The spirometry will be centrally read.

Spirometry data will be provided by CLARIO.

Reversibility test

A reversibility test will be administered following pulmonary function testing after asthma medications have been withheld for the appropriate intervals. Participants will receive 2 to 4 puffs of albuterol/salbutamol from a primed metered dose inhaler (MDI). Alternatively, and only if it is consistent with usual office practice (to be documented), reversibility may be performed using inhalation of nebulized albuterol/salbutamol. Spirometry may be repeated several times within 30 minutes after administration of bronchodilator. Reversibility, which is defined as an increase in absolute FEV1 of $\geq 12\%$ over the baseline value, with an absolute increase of at least 200 mL, must be demonstrated within 30 minutes of bronchodilator administration. If the participant does not meet the reversibility at SV1, up to 3 repeat attempts can be performed at any time during screening, prior to the randomization visit (Visit 2). This is only required if a reversibility test meeting eligibility criterion was not performed within 6 months prior to SV1.

15.9.2. Center Assisted Assessments

[REDACTED]

[REDACTED]

[REDACTED]

[REDACTED]

[REDACTED]

[REDACTED]

[REDACTED]

[REDACTED]

[REDACTED]

Actigraphy data

Wrist actigraphy is a technique for measuring movement of a limb over an extended recording period (days to weeks). The signals generated by wrist movement are sensed by a tiny microcomputer contained within the watch (See Protocol [Section 8.1.1](#)) and translated into activity counts.

The device (Actiwatch) is being worn on the wrist of the non-dominant hand in this study to provide estimates of the duration, timing, and patterns of sleep in study participants (i.e., [REDACTED], WASO, and [REDACTED]). Eligible participants will be trained on how to use the Actiwatch and will complete assessments from Day -11 to Day -1 (right before Day 1); the assessments performed at the same date as Day 1 will be taken into account for baseline calculation only if the end time of assessment is before 12 pm, reflecting the last night before the visit; daily assessment thereafter until Week 4; then only the week before a clinical visit until EOT.

An operational manual will be provided to the Investigators.

Actigraphy data score will be directly provided by KONEKSA.

15.10. Rescue and Prohibited Medications.

Rescue medications (i.e., reliever medications) will be identified from the "Asthma Reliever Medication" eCRF page.

In the table summary, rescue medications will be categorized into SABA (ATC class R03AC), systemic corticosteroids (ATC class H02AB) or Other.

Treatment with following medications is considered as prohibited prior to the first IMP intake (including prior the study entry) and when taken concomitantly with the IMP:

- Any biologic therapy (including experimental treatments) or systemic immunosuppressive drugs

[figure not shown]
- Treatment with systemic corticosteroids (systemic corticosteroids can only be used to treat an asthma exacerbation, and are not allowed to be used for other conditions)*
- Live (attenuated) vaccine**
- Sedative, anxiolytic, or hypnotic treatments (including melatonin)
- Systemic sedative antihistamines (except the newer generations of antihistamines like cetirizine, loratadine and fexofenadine)
- Theophylline
- Lipophilic beta blockers, Opioids, Clonidine, Antidepressants or other medications known to interfere with sleep***

* For participants recruited before protocol amendment 1, systemic corticosteroids intake is considered as prohibited. For other participants, systemic corticosteroids used to treat an asthma exacerbation are allowed and recorded (i.e., considered as rescue medication, not prohibited).

** Also considered as prohibited after the last IMP intake, up to the end of the study.

*** Note: In most cases, chronic treatments administered regularly and at stable dosing are acceptable. Investigators should assess the degree to which an individual medication may cause changes in sleep pattern or sleep quality during the study, compared to the pre-baseline state.

16. SIGNATURE PAGE

Client:	SANOFI
Protocol Number:	LPS16677
Document Description:	Final Statistical Analysis Plan
SAP Title:	A Phase 4, randomized, double-blind, placebo-controlled, multicenter, parallel-group study of the effect of dupilumab on sleep disturbance in patients with uncontrolled persistent asthma
SAP Version Number:	2.0
Effective Date:	24 FEB 2022
Author(s):	
	
Approved by:	
	
	

ADDENDUM TO STATISTICAL ANALYSIS PLAN FOR LPS16677

The SAP was approved in February 2022. Due to data issues detected during the course of the study, this addendum provides additional data handling rules not included in the SAP approved.

#1 In [Section 15.8](#) of SAP: Handling rule of duplicates records for daily questionnaires

There are many duplicate records for daily questionnaires remotely completed by phone (Asthma sleep disturbance questionnaire/sleep diary/ANS/ADSD). The duplicates (same participant, question, date, but with different time/answer provided) will have to be managed at ADaM level.

The rule to select the most appropriate record is as the followings:

1. To select the most frequently recorded response for a given patient/question/day.
2. If it does not enable to identify a unique response (eg, 2 different answers submitted 2 times), then the earliest submission (based on recorded time) will be selected.

#2 In [Section 15.8](#) of SAP: Handling of Sleep Diary Data

Sleep diary is one of the PRO questionnaires in LPS16677 with the following questions:

- 1: Select the number that best describes the quality of your sleep last night
- 2a: Approximately what time did you start trying to fall asleep last night?
- 2b: Approximately what time did you fall asleep last night?
3. Approximately how many times did you wake up last night (not including when you woke up for the day today)? Record “0” if you do not remember waking up last night.
4. Considering all the times you woke up last night, how much time were you awake in total? Record “0” if you do not remember waking up last night.
- 5: At what time did you wake up for the day today?
6. Select the number that best describes how rested you felt when you got up for the day today.

During the ongoing blinded data review, illogical/inconsistent responses to these questions have been identified within the same participant and questionnaire submission. For example, time falling asleep is recorded to occur before trying to fall asleep, time waking up is recorded to occur before time of falling asleep, total sleep time is recorded as being longer than the time in bed, etc.

In order to remove the illogical responses in the derivation of sleep related endpoints, the following rules will be applied:

- A. For questions related to previous night (2a and 2b), if the recorded time lies between 12:00 and 23:59 then set the date equal to the day before the questionnaire was completed. Otherwise set date equal the day questionnaire was completed.
- B. Additionally, the following conditions will be checked:
 1. “Date/Time Did You Wake Up Today” must be equal or later than “Date/Time Fall Asleep Last Night”
 2. “Date/Time Did You Wake Up Today” must be later than “Date/Time Try Fall Asleep Last Night”

3. “Date/Time Did You Wake Up Today” minus “Date/Time Fall Asleep Last Night” must be equal or greater than WASO which is “Time awake after initial sleep onset but before the final awakening” and is the response to Question 4.
4. “Date/Time Fall Asleep Last Night” must be equal or later than “Date/Time Try Fall Asleep Last Night”
5. WASO is equal or greater than zero.

If any of the above conditions fail, then the data collected on that day will not be considered in the derivations.

Once the above rules are applied, the following parameters will be derived (except for WASO which is collected directly from the questionnaire) and used for analysis:

WASO = Wake After Sleep Onset = Time awake after initial sleep onset but before the final awakening

#3 The team noted some typo in PROMIS conversion table (raw-score to t-score) in the [section 15.8](#) of SAP for LPS16677 – Morpheo study.

Please see corrections below:

- Raw-score = 9 => t-score = 35.2
- Raw-score = 37 => t-score = 73.4
- Raw-score = 40 => t-score = 80.1

#4 In [section 8.1.4](#), it is indicated that SCS rescue medications will be identified using CDGsn00010. The medical team discussed this point, and finally decided to use ATC code to identify SCS from rescue medication page (Asthma Reliever page) to keep consistency with [section 15.10](#) (ie, CDGsn00010 will finally not be used).

#5 Asthma Control Questionnaire ( and ACQ-5) in [section 15.3](#):

In the final approved SAP, it is indicated that if only one question has missing score, it will be interpolated following the example below:

$$(\text{Sum of score at Visit 4}/\text{sum of scores excluding question 5 at Visit 3}) \times \text{score of question 5 at Visit 3.}$$

This will be done, except in rare cases where the sum of scores excluding the missing question at the previous visit is 0. In that case, the missing question will not be imputed at the current visit.

#6 The final SAP approved in February 2022 was developed based on Amended Protocol 1, Version 1.0 dated September 17th, 2020. Contents of final approved SAP [Section 13](#) reflects the changes performed in SAP compared to this amended protocol 1. After the SAP has been signed, a new protocol amendment

was performed (Amended Protocol 2, Version 2.0, dated September 26th 2022). All the changes mentioned in [Section 13](#) from SAP have been implemented in this amended protocol v2.0.

#7 If multiple records are available for a same participant at the same date, the earliest record (based on recorded time) will be used for the analysis.

#8 No further analyses are planned for patients recruited by Metasite (Science37) mentioned in protocol amendment v2.0.

#9 The following modifications of prohibited medications identification rules ([Section 15.10](#)) will be implemented based on medical team review:

1. Any medication that started after the EOT visit is not prohibited except for the Live (attenuated) vaccines that are prohibited until the EOS visit.
2. Blinded medical review will be conducted in order to confirm (or not) prohibited status for those medications identified as prohibited using programming rules. Only the medications confirmed as prohibited during the medical review will be presented in the analysis.

In those tables (both prior and concomitant prohibited medications), "Medication type" is determined as per CDG (ie, 1 CDG = 1 "Medication type").

#10 The following modifications of AESI identification rules will be implemented

1. Anaphylactic reactions: includes anaphylactic reaction using CMQ name CMQsn00021 and programmatic identification of cases based on occurrence of at least two events meeting the algorithm criteria occurring within 2 consecutive days of each other. The latter cases identified using the algorithm will undergo blinded medical review taking into account the timing of events relative to each other and to IMP administration for final determination of an anaphylactic reaction or not.
2. Systemic hypersensitivity reactions: CMQ name CMQsn00214 and [AE corrective treatment/therapy='Y' or Action taken with IMP='Drug withdrawn' or Action taken with IMP='Drug interrupted'] followed by blinded medical review (documented process) for selection of relevant systemic hypersensitivity events
3. Any severe type of conjunctivitis or blepharitis: Based on the CMQ names CMQ10498 and CMQ10497 with "Severe" ticked in Adverse Events eCRF page.
4. Helminthic infections: Based on CMQ name CMQ10548.
5. Keratitis: Based on CMQ name CMQ10642.
6. Clinically symptomatic eosinophilia: based on CMQ name CMQ10641 followed by blinded medical review (documented process) for selection of relevant eosinophilia events.
7. ALT increase: based on the CMQ names CMQ00029 with the addition of "Is the event an AESI" answered YES on AE eCRF as reported by the investigator.

For AESI Anaphylactic reactions, Clinically symptomatic eosinophilia and Systemic hypersensitivity reactions: blinded medical review will be conducted in order to confirm (or not) AESI status for those AEs identified as AESI using programming rules. Only the AEs confirmed as AESI during the medical review will be presented in the analysis.

#11 The codelist to identify Atopic comorbidities is updated, CMQs CMQ10440, CMQ10539 and CMQ10538 have been replaced by CMQ10799 and CMQ10800 to get more appropriate terms.

#12 In accordance with the general changes made to all Dupi studies, the following changes are made:

1. TEAE period is defined as the time from the first administration of the IMP to the last administration of the IMP + 98 days (instead of 84 days in [Section 9](#) from approved SAP);
2. Concomitant medication is defined as any treatments received concomitantly to the IMP, starting from the date of first IMP administration to the date of last administration + 98 days (instead of 14 days in [Section 7.1.2](#) from approved SAP).

#13 As stratification factors are generally used separately in modeling, both Region (Eastern Europe, rest of world [ROW]) and baseline ICS Dose (high, medium) variables will be included separately in all MMRM models to replace the single variable of stratum (Eastern Europe with high ICS dose, Eastern Europe with medium ICS dose, ROW with high ICS dose and ROW with medium ICS dose).

#14 As only 1 participant has been recruited in [REDACTED], inclusion in [REDACTED] (YES/NO) is removed from the covariate list in all analytic models. Also, [REDACTED] data will be presented as listings instead of being summarized through descriptive statistics.

#15 [Section 8.2](#), qualitative descriptive analysis by visits showing number/proportion of participants in each category will be displayed for [REDACTED] (“Poor”, “Fair”, “Good”, “Very good”, “Excellent”), [REDACTED] (“very much better”, “moderately better”, “a little better”, “no change”, “a little worse”, “moderately worse”, “very much worse”) and [REDACTED] (adequately controlled [score <= 1.0], inadequately controlled [score > 1]).

#16 [Section 15.8](#), under Asthma Control Questionnaire ([REDACTED] and ACQ-5), MCID is not an appropriate wording, thus the following clarifications revisions are made.

- “On the 7-point scale of the [REDACTED], a change or difference in score of 0.5 is the smallest change that can be considered clinically important, corresponding to the Minimal Clinically Important Difference (MCID) defined by the developer” is replaced by “On the 7-point scale of the [REDACTED] a change or difference in score of 0.5 represents the within-patient change that can be considered clinically meaningful”.
- “On the 7-point scale of the ACQ-5, a change or difference in score of 0.5 is the smallest change that can be considered clinically important, corresponding to the MCID” is replaced by “On the 7-point scale of the ACQ-5, a change or difference in score of 0.5 represents the within-patient change threshold that can be considered clinically meaningful.”

#17 [Section 8.1.4](#) Subgroup Analysis, listed subgroups may be combined due to small sample size or modified based on actual data collected. For instance, number of severe asthma exacerbation events (1, 2, >2) within 1 year prior to the study will be combined into 2 subgroups (1, >=2) instead of the proposed 3 subgroups; number of controller medications at study entry will be modified from (2, 3) to (2, >=3) to include participants who used more than 3 controllers.

#18 For the Participant [REDACTED] recruited in [REDACTED], stratification factors entered into the IVRS system (Region = “All” / ICS dose = “All”) do not match with expectations and do not enable to include the participant in the analyses as appropriate. In order to fix this issue and include this participant in the analyses, new specific variables will be derived for Region and ICS dose:

- For the participant [REDACTED]: Based on external file provided by sponsor (in which Region and ICS dose level are determined according to information recorded in the database)
- For all other participants: Based on values recorded in IVRS.

#19 Section 5.2 Protocol deviations. The following modification will be made: Category “potentially impacting efficacy” removed and category “Impact due to war in Ukraine” added.

The paragraph “All critical or major protocol deviations potentially impacting efficacy analyses (including randomization and drug-dispensing irregularities; see [Table 5-1](#) Randomization and drug dispensing irregularities), and other major or critical deviations will be summarized overall and according to COVID-19 impact (i.e., deviations related to COVID-19 pandemic) for the ITT analysis set by study intervention group and overall using number and percentage.” is replaced by “All critical or major protocol deviations (including randomization and drug-dispensing irregularities; see [Table 5-1](#) Randomization and drug dispensing irregularities) will be summarized overall and according to COVID-19 impact (i.e., deviations related to COVID-19 pandemic) as well as impact due to war in Ukraine for the ITT analysis set by study intervention group and overall using number and percentage.”

#20 Section 7.2.1 Extent of exposure. As definition for duration of exposure is taking into account last IMP + 14 days, the analysis by categories will be modified to capture appropriately the participants that took their treatment up to the end. The category “> 12 weeks” will be replaced by “>12 and <=14 weeks” and “>14 weeks” (and in cumulative analysis, category “>14 weeks” will be added)

#21 Section 5.1 Disposition. In the approved SAP, it is written: “A summary table to show participant disposition by visit according to trial impact (disruption) due to COVID-19 (visit not done, visit partially done on site, visit partially done by phone and visit done but delayed) will be provided overall and by country for the ITT analysis set”.

To avoid confusion with participants included in the subgroup [trial impact (disruption) due to COVID-19], it should be replaced as follows: “A summary table to reflect COVID-19 impact at each visit (visit not done, visit partially done on site, visit partially done by phone and visit done but delayed) will be provided overall and by country for the ITT analysis set”. And title of the corresponding table updated accordingly.

Signature Page for VV-CLIN-0655407 v1.0

lps16677-16-1-9-sap-addendum

Approve & eSign

Approve & eSign

Approve & eSign

Sanofi
Protocol: LPS16677

Dupilumab
Clinical study report

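### SAP Addendum #1, #2 and #7 do not say how duplicate Sleep Diary submissions and logic checks combine, so a day with a valid submission can be voided and, with three or more submissions, a night nobody reported can be assembled

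*SAP*

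**What the plan says.** Three items of the SAP Addendum bear on this.

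- **#1 (duplicates).** The addendum reports that "There are many duplicate records for daily questionnaires remotely completed by phone", naming the Asthma Sleep Disturbance Questionnaire, Sleep Diary, ANSD and ADSD. It defines the problem per question: "The duplicates (same participant, question, date, but with different time/answer provided) will have to be managed at ADaM level". Rule 1 is "To select the most frequently recorded response for a given patient/question/day". Rule 2 covers the case with no unique answer: "then the earliest submission (based on recorded time) will be selected". Nothing requires the answers kept for one night to come from one submission.
- **#2 (Sleep Diary logic).** Illogical answers "have been identified within the same participant and questionnaire submission". Conditions B1 to B5 compare attempt time (2a), onset time (2b), time awake (Question 4, WASO) and wake time (Question 5). In B3, for example, wake time minus onset time "must be equal or greater than WASO which is" the answer to Question 4. The consequence is at day level: "If any of the above conditions fail, then the data collected on that day will not be considered in the derivations".
- **#7 (multiple records).** For several records from one participant on one date, "the earliest record (based on recorded time) will be used for the analysis". No scope is given, and #1 is not mentioned.

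SAP 8.2.1 takes the number of nocturnal awakenings from Sleep Diary Question 3. SAP 8.2.13 places that endpoint second in the hierarchical test sequence, after the primary endpoint.

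**The concern.** The Sleep Diary answers for one night describe a single sequence of events: when the participant tried to sleep, fell asleep, was awake and got up. Checks B1 to B4 test whether those answers fit together. A rule that chooses each answer separately can break the fit, or can retain a broken entry when a sound one was submitted the same day. The day-level consequence in #2 then removes everything recorded for that day.

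The sponsor's own data review reports both ingredients: many duplicates, and illogical answers inside a submission. At stake are usable nights for the Sleep Diary endpoints: nocturnal awakenings (alpha-controlled), WASO, sleep quality and restorative sleep. Question 3 is not itself tested by B1 to B5, but on the plain wording of #2 it is lost with the rest of the day. A mixed night that happens to pass the checks would enter the WASO and timing data with nothing to flag it.

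**Working it through.** The plan gives no figure to reproduce, so the check applies the rules as written to constructed nights. It assumes #1 is applied before #2, which the numbering and the use of one answer per question suggest but the text does not state.

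**1. Two submissions, the first illogical.**
- First: attempt 23:00, onset 22:30. Second: attempt 22:00, onset 22:30. Both have WASO 20 min and wake time 06:00.
- The first fails B4 (22:30 is before 23:00); the second passes all five checks.
- Attempt time is a 1:1 tie, so rule 2 keeps the first entry's answer. The result is the first entry whole. It fails B4 and the day is voided.
- Under #7 the earliest record is also the first entry, with the same outcome.
- With two complete submissions every disagreement is a 1:1 tie, so #1 always returns the earlier submission whole. No mixed night can arise.

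**2. Three submissions, all valid, with a tie.** In order of submission, attempt/onset is 22:00/22:30, 23:00/23:20, 23:00/23:40.
- Attempt: 23:00 occurs twice, so 23:00.
- Onset: three different answers, so the first submission's 22:30.
- B4 needs onset no earlier than attempt. 22:30 is before 23:00, so the day is voided.
- This depends on order: it fails in the 2 of 6 orders where 22:00/22:30 came first. In the other 4, #1 returns a real submission, which passes.

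**3. Three submissions, all valid, no tie.** Attempt is 21:45 throughout.

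| Submission | Onset | Wake | Wake minus onset | WASO | B3 |
|---|---|---|---|---|---|
| A | 22:00 | 06:00 | 480 min | 300 min | passes |
| B | 03:00 | 06:00 | 180 min | 60 min | passes |
| C | 03:00 | 09:00 | 360 min | 300 min | passes |
| Selected by #1 | 03:00 (B, C) | 06:00 (A, B) | 180 min | 300 min (A, C) | fails |

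Each selected value is a unique mode, so the tie-break is not used and the day is voided in all 6 orders.

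**4. Enumeration on an illustrative grid.** Two possible values for each of 2a, 2b, Question 4 and Question 5 give 2^4 = 16 records. All ordered sets of k submissions were run through #1 and then B1 to B5.

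| k | Sets | Mixed night | Voided with a valid submission present | Voided among all-valid sets |
|---|---|---|---|---|
| 2 | 256 | 0 | 60 | 0 of 100 |
| 3 | 4,096 | 960 | 1,320 | 24 of 1,000 |
| 4 | 65,536 | 12,288 | 23,280 | 216 of 10,000 |

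Keeping only the earliest record, as #7 would, voids the same numbers with a valid submission present on this grid: 60, 1,320 and 23,280. These are counts of possibilities, not prevalences.

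**5. Sensitivity of the mixed-night share.** Simulation of three submissions of 7 items, each item changed independently to a distinct value with probability p, gives mixed nights on about 3% of such days at p = 0.05, 13% at 0.1, 42% at 0.2 and 61% at 0.3. The share depends almost entirely on the assumed p, for which the documents give no basis.

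**6. The reverse order.** If #2 ran first on its literal day-level wording, one failing submission would still void the day. If only failing submissions were removed, #1 could still mix the remaining valid ones, and the result would go unchecked.

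**The case against.** - **#7 may govern.** If it applies to the daily diaries, mixed nights cannot occur. That stands, but the case of an illogical first entry and a valid re-entry remains. #7 also contradicts #1, and the addendum does not say which prevails.
- **Rule 2 may mean the whole earliest submission.** Example 2 would then return 22:00/22:30 intact and pass. Example 3 uses no tie-break and is unaffected.
- **The earliest entry is a defensible choice for recall.** The diary is meant to be completed on waking. That is a fair reason to prefer the first entry when it is usable. It carries little weight when the first entry fails the checks, because the plan then discards it anyway.
- **Baseline is protected.** A reader might infer that voided days readily cost participants their baseline. SAP 4.4.6 does not support that: with fewer than 4 measurements in the 7-day window, the most recent 4 are used, and SAP 15.8 has the diary collected for 11 days before the baseline visit. Baseline is missing only if fewer than 4 usable entries remain.
- **The extent is unknown.** Mixed nights need at least three submissions on one day, and no count of duplicate days or submissions per day is given. A reader might take one simulated percentage as an estimate of frequency; the documents do not support that.
- **No bias is shown.** The inconsistencies were found in blinded data review, and the rules do not refer to treatment arm.

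**Conclusion.** The concern holds as a gap in the derivation rules. As written, #1 followed by #2 voids a day whose first entry is illogical even when a valid second entry exists, and #7 gives the same result. With three or more submissions, #1 can also assemble a night that no submission contains. That night may fail the checks although every submission passes, or may pass them unnoticed.

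The effect on results cannot be computed from the documents and is probably small. Single nights are diluted in averages over up to 28 days (SAP 8), and the baseline fallback limits baseline loss. It would be wrong to infer that the primary endpoint is compromised: the Asthma Sleep Disturbance Questionnaire is a single item, cannot become a mixture, and is not subject to the #2 checks.

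Two assumptions matter. That #1 precedes #2 is an inference, though the reverse order does not remove the problem. That nocturnal awakenings, sleep quality and restorative sleep are lost with a voided day follows from the plain wording of #2; if #2 was meant only for WASO and the timing variables, the exposure is narrower. This is a low-severity, inexpensive improvement.

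**What to change.** For the Sleep Diary, state the unit and the order explicitly:

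1. Apply rule A and checks B1 to B5 to each whole submission.
2. Drop the submissions that fail.
3. Among those left, keep the most frequent identical submission, or the earliest valid one if there is none.
4. Exclude the day only if no submission passes.

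Select ADSD and ANSD duplicates by whole submission too, since their six items can be mixed in the same way and have no logic check. Rule #1 can stay for the single-item Asthma Sleep Disturbance Questionnaire. State that #7 does not apply to the daily questionnaires.

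Under this rule mixed nights cannot occur and no Sleep Diary day with a valid submission is lost; examples 1 to 3 above are all kept. The cost is a change in the unit of selection and in the order of two derivation steps. It needs no new data and can be specified blind. The downside is that on some days a later same-day entry is used.
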